6.7 Monitoring plan

The study will be monitored separately in the two centers. In Denmark, it is intended that the study is monitored by GCP-enheden ved Københavns Universitetshospital. In Sweden, the study is intended to be monitored by Gothia Forum for Clinical Studies. Both are units serving the respective regional healthcare researchers.

As the monitoring unit in the region of the sponsor's center, the Danish GCP unit will have the responsibility to coordinate a shared monitoring plan, where each party monitors the investigation center. The monitoring plan will be made with due consideration to the centers designated tasks and reflect considerations to specific risks in the tasks performed.

An overview of monitoring activities and focus-areas are given in Table 4.

Investigation activity	Stage / Visit	GCP Unit KU, DK	Gothia Forum, SE
Monitoring plan	Before	Х	(x)
Initiation of study	Before	Х	Х
Recruitment	Before	Х	Х
Screening and inclusion/exclusion	Visit 1	Х	Х
Selection and documentation of lesions for treatment	Visit 2	Х	Х
HIFU Treatment	Visit 2	Х	Х
Post treatment documentation and evaluation by investigator and patient	Visit 2	Х	Х
Follow-up visits with documentation and evaluation by investigator and patient	Visit 3 - 6	Х	Х
Ultrasound scanning – Procedure and analysis from measurements	Visit 2 – 6	Х	
Biopsies – Procedure and analysis from pathological report	Visit 2 – 4		Х
CRF entry and REDcap	Visit 1 - 6	Х	Х
Statistical analysis	After		Х
Study Reporting	After	х	
Close of study – Archive readiness	After	Х	Х

lable 4. Monitoring	activities in the two	o monitorina unite	s used by the	e investigation centers.

7 Statistical design and analysis

The number of patients recruited for participation in the study will be balanced with due consideration to ethical aspects and the statistical background for conclusive statements regarding the primary endpoint.

As mentioned above, the primary endpoint of the study is to document the tolerability and safety profile of the treatment. As the main measurable endpoint, the grade of overall adverse effects following treatment is best suited for evaluation of participants in the study. The measurement of this endpoint is done subjectively by the investigator according to a conventional grading system, and is measured directly after treatment and at all subsequent control visits. The input template for measurement is illustrated in Fig. 7.

Investigator overall scoring of treatment side effect severity (one X)									
Absent / Normal Mild Moderate Severe Life-threatening or disabling Death									
Grade 0	Grade 1	Grade 2	Grade 3	Grade 4	Grade 5				

Fig 7. The primary end-point of the study is the investigator's grading of adverse effects following treatment as measured directly after treatment and in all subsequent patient follow-up visits.

According to the defined endpoint, the minimum number of patients must therefore be calculated to support a sufficiently high power for the statement that not more than 30% of patients will experience an overall side-effect of Grade 3 or above based on Common Terminology Criteria for Adverse Events (CTCAE), U.S. Department of health and human services, Ver 5.0, Nov 27, 2017.

Secondary endpoints regarding efficacy, feasibility etc. are also measured and analyzed throughout the study, and form important data for analysis, but are not included in the calculation of the minimum number of patients.

To obtain an initial indication of the necessary number of participants needed in the study, a simple estimation based on the conventional calculation of sample size to estimate a proportion or apparent prevalence with specified precision can be used.

A simple binary outcome is considered:

- Accept: Participants have Grade 2 side effects or lower
- Reject: Participants have Grade 3 side effects or higher

Based on substantial previous clinical experience with the study device (used for other skin treatments), severe side effects and adverse events are very rare, and an estimated proportion of 90% having Grade 2 or lower side-effects is therefore a reasonable starting point for the calculation (P=0.90).

As the measurement of side-effects by the investigator is subjective and with a quite course resolution, a total error can be set to 30% (e = ± 0.15), roughly reflecting the interval between the six possible gradings. A standard confidence interval of 95% can be used (Z = 1.96).

At these inputs, the minimum population for the investigation can be calculated as follows:

$$N = (Z^2 \times P \times (1 - P))/e^2 = (1.96^2 \times 0.90 \times (1 - 0.90)/0.15^2) = 15.37$$

At 16 participants in the study, it is therefore possible to say with 95% confidence that the results of treatments will fall within the acceptable group. The minimum number of participants at various other proportions is shown in Table 2.

Table 2. Calculated minimum population in an investigation for obtaining statistical significance at a cure rate of p and with a error of $\pm 15\%$

р	0,95	0,90	0,85	0,80	0,75	0,70	0,65	0,60	0,55	0,50
Ν	9	16	22	28	33	36	39	41	43	43

In a second step, power curves can be calculated against an alternative base-line of equal proportions having acceptable and rejectable grades of side-effects (the null hypothesis).

Fig 8. shows the power curve for the study containing the above minimum 16 participants as a function of the actual obtained passed AE-profiles. At the hypothesis of 90% having an acceptable AE-profile after HIFU treatment the power is calculated to be 71%.

Similarly, curves correlating the number of necessary participants at fixed power-levels of 80% and 90% at the hypothesized 90% having an acceptable AE-profile after HIFU treatment can be calculated. As shown in Fig. 9, the study will require 20 participants if a power of 80% is needed, while 26 participants will be needed to reach a power of 90%.

[figure not shown]

Fig. 8. Power curve showing the probability of being able to detect difference between HIFU treatment with 90% passed AE profile against a baseline treatment with 50% acceptable proportion. At the projected succes rate of 90%, the difference in cure rate can be detected with a 95% confidence level and power of above 71% if the population in the investigation is 16 participants.

[figure not shown]

Fig. 9. Power curves showing the necessary population to obtain power levels of 80% and 90%. At the projected acceptable AE-profile of 90%, the hypothesis can be confirmed with a power of 80% probability if the population is 20 participants and a poer of 90% if the population in the investigation is 26 participants.

In conclusion, the statistical analysis shows that participation as low as 16 patients will give an acceptable power, provided the AE profile is in the expected range. At worse AE-profiles, or requirements for a higher power-level in comparison with alternatives, the required population size naturally increases, and populations above 20 will typically needed.

In consideration of the status as an initial tolerability and feasibility study performed on a relatively young population group with low expected drop-out, it is considered that a total of **20 participants distributed among the two centers** will be a well-balanced population taking ethical, clinical and practical issues into due consideration.

It should finally be mentioned that each participant will present a minimum of 4 tumors for treatment, and sometimes significantly more than this. The total number of treated tumors in the study will thus be high. Under certain assumptions, this allows for pooling of data on separate tumors during the data-analysis phase, rather than looking at combined reactions and results on participant-level only. The CRF in the study accommodates such individual data collection.

8 Data management

The study shall respect all legal requirements regarding data protection of the participant, with the necessary exceptions specified in the study consent form. As a study conducted by two centers in

the EU, the overall framework of the European Regulation on General Data Protection Regulation 2016/679 (GDPR) with its respective national adaptations will govern data management.

In Denmark, all information about participants is subjected to "Lov om behandling af personoplysninger" and "Sundhedsloven", and these will be complied. The approval from Danish Data Proctection Agency (dataanmeldelse i Region Hovedstaden) will be applied.

In Sweden, all information about participants is participanted to The General Data Protection Regulation of the EU, and "25 kap. 11 § 5 p. offentlighets- och sekretesslagen (2009:400) (OSL)", and these will be complied. The approval from Etikprövningsmyndigheten will be applied.

Each participant will be informed that representatives from the respective national data protection agency and Medicines Agency may inspect their medical journals and trial records, in all confidentiality. The requirements to ensure anonymity of data, data security and confidentiality of data will be explained to the participants and complied.

All information will be treated with strict confidentiality and stored as confidential material according to the respective national regulations. Only the principal- and coordinating investigators will have access to the information.

Study results will be reported in anonymous form. The investigator will keep identification lists of all participants. This list will include full name and social security number.

The recorded data will be kept in a Case Report Form and an individual journal will be created for the investigation. The information will only be available for inspection for authorized representatives from the relevant authorities upon request (national GCP Unit, Data Protecting Agency, Medicines Authority).

During the investigation, paper-based CRF will be used. All information according to protocol and collected during the study must be entered in the appropriate field of the CRF. The investigator, or designated representative, should complete the appropriate CRF fields as soon as possible after information is collected. The information must match the information that exists as source documents in the clinic chart, hospital chart, and/or investigator's files. An explanation should be given for all missing data. REDCap will be used for storage of such information afterwards.

The investigators in each center will retain investigational records, copies of CRF and source documentation for the maximum period required by the regulatory authorities.

The center in Denmark will be appointed as data-processor. Only pseudonymized data will be transmitted from the center in Sweden to Denmark for combined processing and reporting. A cooperation agreement including encrypting of the files and relevant provisions for data transfer and management will be made between the two centers to ensure that transfer of such data is in compliance with GDPR and the legislative requirements in both countries.

It is the coordinating and principal investigators at each center responsibility to assure the accurate completion, review, and approval of all CRFs, and the timely completion and submission of all adverse event forms.

In the case of a personal data breach, the relevant investigator(s) must without undue delay and, where feasible no later than 72 hours after having become aware of it, notify the personal data breach to the respective national Data Protection Agency, unless the personal data breach is unlikely to present a risk to the affected individuals.

Reporting must be done as per the national guidelines, e.g. via electronic log-in to the relevant portals.

9 Amendments to the CIP

If the sponsor intends to introduce modifications to a clinical investigation that are likely to have a substantial impact on the safety, health or rights of the subjects or on the robustness or reliability of the clinical data generated by the investigation, it shall notify, within one week, the relevant national authorities in Denmark and Sweden of the reasons for and the nature of those modifications.

The sponsor shall include an updated version of the relevant documentation as part of the notification. Changes to the relevant documentation shall be clearly identifiable.

The relevant authorities in Denmark and Sweden shall assess any substantial modification to the clinical investigation.

The sponsor may implement the modifications at the earliest 38 days after the notification unless:

- a) A medical authority in Denmark or Sweden has notified the sponsor of its refusal based on the grounds referred to in MDR Article 71(4) or on considerations of public health, subject and user safety or health, of public policy, or
- b) An ethics committee in Denmark or Sweden has issued a negative opinion in relation to the substantial modification to the clinical investigation, which, in accordance with national law, is valid for that entire country.

The relevant authorities concerned may extend the period for decision by a further seven days, for the purpose of consulting with experts.

10 Deviations from clinical investigation plan

Deviations to the CIP are not allowed unless they affect the subjects' rights, safety and well-being, or affect the scientific integrity of the investigation.

Deviations needed to protect the rights, safety and well-being of human subjects under emergency circumstances may proceed without prior approval of the sponsor and the relevant authorities.

Deviations, which are systematic, necessary, and significant to the study, i.e. affect the subjects' rights, safety and well-being, require a protocol amendment with submission and approval from the relevant authorities.

Insignificant, minor and unsystematic deviations to the CIP incurred to maintain the scientific integrity of the investigation, need notification in the case report only.

All deviations must be documented and reported to the sponsor, and must be included in the case report of the day of the visit or the deviation. All deviations shall made available for study monitor's inspection.

11 Device accountability

The sponsor is responsible for registration of the accounts of the device, properly documented. Delivery, placement and return of device has no special risk of hazard and needs no special procedure. No special risk of fire or contamination is noted.

12 Statements of compliance

The sponsor carries responsibility that statements signed by the participating centers/investigators on the fulfilment of the study in accordance with the Declaration of Helsinki, regional and national regulations and any relevant authority or legal requirement. The statements are kept in a study master file.

The equipment supplier shall provide insurance of hazards and accidents related to the use of the device in the study. Hazards and accidents independent of the device and related to the hospital setting are covered by the standard insurance of the hospital. Any hazard or accident in a participant is reported in the participants' patient file belonging to the hospital, and as adverse event in the case report.

13 Informed consent process

Candidates for the investigation are hospital patients referred to the participating departments for a cNF tumor. They all are registered in the standard electronic hospital files.

Potential candidates are informed orally and in writing about the investigation using the standard information of the study submitted to Lægemiddelstyrelsen and the Danish National Committee for Health Research Ethics.

Oral information is provided at an information-meeting with the participating investigator(s). The candidate will be informed in advance that he/she is allowed to bring an assessor for the meeting. The meeting will be held in a room that will only be used for this purpose to avoid unnecessary disturbances. The written information includes investigation participation document as well as relevant information folders from the respective national authorities. In Denmark this includes the document "Dine rettigheder som forsøgsperson" from "De Videnskabsetiske Medicinske Komiteer (VMK)". In Sweden this includes printed information for research persons which will be accepted by Etikprövningsmyndigheten pror to the study.

The informed consent form will include all the elements that are required according to the respective national legislation. If the participant wishes to participate, a new appointment will be booked where the doctor and the participant sign the consent. The new appointment and time of reflection will be within 2-7 days after the first appointment (allowing more than the required 24 hours of reflection time), but if the patient needs more time of reflection this can also be accommodated. If the patient wishes to sign the content at the first appointment this is also acceptable. If the patient fulfills all in-and exclusion criteria the patient will be included.

After the information-meeting, all active participants will be updated with any new and important information or change in the study that can have influence on the participants' willingness to participate or safety. The approved documents will be updated accordingly.

Oral information is repeated on the inclusion visit (visit 1 in the CRF), with opportunity for the patient to ask questions. The consent form is signed after the patient has declared the full understanding of the information and the study concluded as acceptance to enter study. In the oral information individual aspects of special relevance to the participant shall be emphasized.

Participants who are not able to understand the information cannot be included in the study. The signed and qualified acceptance of the participant to volunteer for the study is filed in the case report form book.

14 Adverse events, adverse device effects, and device deficiency.

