5.1 Primary endpoint - Tolerability

- The grade of any adverse events (AE) requiring medical intervention within three months of treatment should be low. Device-based treatment will be considered tolerable if less than 30% of participants treated have an "Overall AE Score" larger than Grade 2 AE at the 3month follow-up (visit 4) as assessed via Common Terminology Criteria for Adverse Events (CTCAE), U.S. Department of health and human services, Ver 5.0, Nov 27, 2017.
- The rate and nature of spontaneous healing of the treated cNF lesion and any safety related event including potential wound formation and wound healing should be equivalent to expectations from alternative method(s). Safety evaluation includes rating of treatment associated sequele by end of study, e.g. dyspigmentation and scarring and overall investigator rating compared to expectations.

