5.2 Secondary endpoints – Efficacy, safety and feasibility

- Efficacy: Rate of clearance, e.g. reduction of tumor mass of treated cNFs based on 2D and 3D photography or ultrasound imaging assessment at 3 and 9 months parallel to assessment of the degree of dyspigmentation with hypermelanosis or hypomelanosis of the lesion and the perilesional untreated skin.
- Safety: Itch and pain from the treatment measured on a 0-10 point numerical scale.
- Safety: Wheal and flare reaction and inflammatory responses are measured on a graded scale.
- Safety: Any objective adverse effect or event, local or systemic, related to the treatment and the investigational device is measured (wound and course of wound healing, scar formation, instrumental hazards) is categorized immediately after treatment and at all follow-up visits.
- Feasibility: Feasibility is evaluated both quantitatively (time spent on treatment) and qualitatively depending on the object considered and cover elements that may compromise or favor HIFU relative to other treatments employed for lesions in clinical practice or from the literature. Feasibility assessment will not produce a direct comparison with alternative methods since the study has no arm with an alternative method. The evaluation comprise the following essentials:
 - 1) Time and resource spent on the treatment session using the device,
 - 2) Investigators' assessment of the practice of using the device and the treatment,
 - 3) Participants" assessment of satisfaction with the treatment and the device.

All skin toxicities will be grated according to the classifications in Common Terminology Criteria for Adverse Events (CTCAE), U.S. Department of health and human services, Ver 5.0, Nov 27, 2017.

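### The primary Overall AE Score is a single subjective cross per participant with no rule tying it to the worst CTCAE-graded event, so a recorded Grade 3 event need not count against tolerability

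*Combined protocol and SAP*

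**What the plan says.** Section 5.1 calls the treatment tolerable if "less than 30% of participants treated have an 'Overall AE Score' larger than Grade 2 AE at the 3month follow-up (visit 4"), assessed with CTCAE v5.0. The sentence before that criterion speaks of adverse events during the three months after treatment.

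Section 7 takes the overall grade as the main measurable endpoint. It says that "The measurement of this endpoint is done subjectively by the investigator according to a conventional grading system" and that it "is measured directly after treatment and at all subsequent control visits". The template in Fig. 7 is headed "Investigator overall scoring of treatment side effect severity (one X") and runs in six steps from absent (Grade 0) to death (Grade 5). Its caption reads: "The primary end-point of the study is the investigator's grading of adverse effects following treatment as measured directly after treatment", and goes on to include the follow-up visits. Section 7 repeats the CTCAE v5.0 reference and splits the result in two. The failing category is: "Reject: Participants have Grade 3 side effects or higher".

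Event-level grading appears elsewhere. Under the secondary endpoints, section 5.2 states: "All skin toxicities will be grated according to the classifications in Common Terminology Criteria for Adverse Events (CTCAE"). Section 14 defines adverse events and their reporting without mentioning the overall score. Section 6.2 allows 3 to 9 treated tumours per participant. Sections 6.1 and 16 describe the study as open-label and unblinded.

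**The concern.** CTCAE grades single events. A participant with several treated tumours and several kinds of event therefore has several grades, and some rule is needed to turn them into one. The plan names the scale but gives no such rule. It asks an unblinded investigator for one overall impression, and no independent review of that impression is described.

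Take a participant with Grade 1 redness at eight tumours and a Grade 3 wound complication at the ninth. One investigator could mark the overall severity as Grade 3. Another could mark it Grade 2, and nothing in the plan makes the second mark wrong. The first participant fails the criterion and the second passes it, with identical event records.

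Timing opens a second route to the same result. If the criterion takes only the mark given at visit 4, a Grade 3 event that occurred and resolved in the first weeks may not enter it, although the same bullet in 5.1 is introduced in terms of the whole three months. At stake is whether the tolerability conclusion can disagree with the trial's own adverse event records.

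**Working it through.** **The plan's own figure.** With P = 0.90, e = 0.15 and Z = 1.96 (section 7): N = 1.96² × 0.90 × 0.10 / 0.15² = 0.3457 / 0.0225 = 15.37, rounded up to 16. This reproduces. It does not depend on how the score is formed, so the fix leaves it unchanged.

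**The texts side by side.**
- Scale: CTCAE v5.0 (5.1 and section 7).
- Form: one cross per participant and assessment (Fig. 7).
- Event-level grades: skin toxicities, as secondary data (5.2).
- Rule linking the cross to the event grades: none in 5.1, 5.2, section 7 or section 14.
- Rule combining the marks from several visits: none. 5.1 points to visit 4, while the Fig. 7 caption covers every visit from treatment onwards.

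**What under-marking could do to the decision.** Inputs: n = 20 (section 6.5.6) and the limit of less than 30% (5.1). Since 6/20 = 30% is not below 30%, a pass needs at most 5 failures. (Section 7 words the limit as inclusive, which would admit a sixth; the wording of 5.1 is used here.)

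Let p be the true proportion of participants with at least one Grade 3+ event, and m the share of them whose primary mark is Grade 2 or lower, through either the global impression or the timing. The counted rate is q = p(1 − m), and

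P(pass) = Σ (k = 0 to 5) C(20, k) q^k (1 − q)^(20 − k).

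The documents give no value for m, so a range is shown. All 20 participants are taken as assessable, and errors as downward only.

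| True rate p | m = 0 | m = 10% | m = 25% | m = 50% |
|---|---|---|---|---|
| 20% | 0.804 | 0.864 | 0.933 | 0.989 |
| 30% | 0.416 | 0.536 | 0.716 | 0.933 |
| 40% | 0.126 | 0.217 | 0.416 | 0.804 |

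For example, p = 0.30 and m = 0.25 give q = 0.30 × 0.75 = 0.225 and P(pass) = 0.716.

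At the planning value, p = 1 − 0.90 = 0.10, P(pass) is 0.989 with m = 0. Under-marking can then add at most 1 − 0.989 = 0.011.

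**The case against.** - **The score is anchored to CTCAE.** This stands. 5.1 and section 7 both name CTCAE v5.0, so it would be wrong to infer that the primary endpoint uses an unrelated scale. What is missing is the step from several event grades to one mark.
- **The reject category may already be an any-event rule.** Read alone, it can be taken that way, and the participant in the example would then fail. In context it dichotomises the overall side-effect grade introduced just before it, which is the one-cross mark. Both readings are available, so the plan is ambiguous. It does not state that a participant with a Grade 3 event is accepted.
- **Nothing says that the cross averages over tumours.** Correct. A reader might infer that one severe reaction is diluted by many mild ones and that the bias must favour a pass. The documents describe no averaging, and an investigator could equally mark the worst reaction.
- **The CRF may contain the rule.** Only the Fig. 7 template is shown, and section 7 says that the CRF takes data on individual tumours. A completion instruction cannot be excluded, but the endpoint definition should carry the rule itself.
- **The sites coordinated their assessment.** Section 6.6 says so in the context of healing and therapeutic effect. That does not supply a rule for this score, but neither do the documents show that the sites will differ.
- **The sample size allows for subjectivity.** Section 7 justifies e = ±0.15 partly on this ground. In the formula, e is a half-width for sampling error and does not correct a systematic shift in marking.
- **A Grade 3 event stays visible.** It would appear in the secondary safety data and, if serious, under sections 14 and 16. It would still not necessarily enter the primary count.

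**Conclusion.** The point holds as a weakness in how the primary endpoint is measured. The score is on the CTCAE scale, but it is one subjective, unblinded mark with no requirement that it be at least the worst recorded grade, and its time window is stated in two ways. The text therefore leaves room for a participant with a recorded Grade 3 event to be counted as acceptable. It does not say that this will happen, how often, or that marks will lean towards a pass.

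The size depends on values that the documents do not give. If the true Grade 3+ rate were 30%, the chance of passing would go from 42% with full counting to 72% or 93% when a quarter or half of those participants are marked lower. At the 10% rate the sponsor expects, the effect is negligible. The weakness matters if tolerability turns out clearly worse than planned, which is the case the criterion exists to detect.

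**What to change.** In 5.1, section 7 and the CRF:

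1. Derive each participant's primary score as the maximum CTCAE v5.0 grade of any adverse event recorded as related to the HIFU treatment or the device, across all treated tumours, from treatment through visit 4. This settles both the aggregation and the time window.
2. Grade all such events by CTCAE, not only skin toxicities.
3. Report complications of the study biopsies in Sweden separately, so that they do not enter the HIFU score.
4. Keep the one-cross global rating as a supportive measure and list any participant in whom it is lower than the derived score.

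The cost is endpoint wording, CTCAE grading of related events outside the skin, and a short derivation. Table 1 already schedules adverse event recording at visits 2 to 6, and section 14.4 already asks for date, resolution and relationship to the device and procedure. The sample size formula is untouched. The downside is that the observed Grade 3+ proportion may be slightly less favourable. Grading and relatedness remain investigator judgements, but each is made on a single event and can be checked against its record.

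### The 95% confidence statement at N = 16 rests on a symmetric normal interval that covers only about 81% at 16 and 88% at 20, and it understates uncertainty on the side facing the 70% limit

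*Combined protocol and SAP*

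**What the plan says.** Section 5.1 calls the treatment tolerable if fewer than 30% of participants have an overall adverse event score above Grade 2 at 3 months. In terms of acceptable outcomes, more than 70% must be Grade 2 or lower.

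Section 7 sizes the study on that yes/no outcome. It describes the first step as "a simple estimation based on the conventional calculation of sample size to estimate a proportion or apparent prevalence with specified precision can be used". It assumes that 90% of participants will have an acceptable outcome, takes Z = 1.96 for 95% confidence, and sets the margin as follows: "a total error can be set to 30% (e = ± 0.15), roughly reflecting the interval between the six possible gradings". The formula is introduced with "At these inputs, the minimum population for the investigation can be calculated as follows" and returns 15.37. The conclusion drawn is: "At 16 participants in the study, it is therefore possible to say with 95% confidence that the results of treatments will fall within the acceptable" category, meaning Grade 2 or lower.

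Table 2 applies the same formula to other proportions, under the caption "Calculated minimum population in an investigation for obtaining statistical significance at a cure rate of p" with an error of ±15%. It gives 9, 16 and 22 participants at p = 0.95, 0.90 and 0.85. A second step then shows power curves. Section 7 still describes 16 as giving acceptable power, but settles on 20 participants in total. No interval method is named for reporting the primary proportion.

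**The concern.** The formula is the half-width of the interval p̂ ± Z·SE, solved for N. That interval needs a reasonable number of outcomes of both kinds. Here 16 × 0.10 = 1.6 Grade 3 or higher outcomes are expected at N = 16, and 20 × 0.10 = 2 at the planned 20. In that range the sampling distribution is skewed and the symmetric interval is a poor description of the uncertainty.

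The margin has a separate weakness. It is justified as "roughly reflecting the interval between the six possible gradings". The spacing of an ordinal grade scale is a matter of measurement resolution. Once the outcome has been cut at Grade 2/3, its sampling error depends on the number of participants and the true proportion, and the spacing of the grades says nothing about either.

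What is at stake is how the primary result is read. True uncertainty is larger below the estimate than above it, and the lower side is the one that faces 70%. A reader who follows the only interval in the plan could conclude that a result is clear of the limit when a valid interval is not.

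**Working it through.** **Inputs.** P = 0.90, e = 0.15, Z = 1.96, planned n = 20 (all section 7). Acceptable level 70% (100% minus the 30% in section 5.1).

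**1. The plan's figure.** N = Z²P(1−P)/e² = 3.8416 × 0.09 / 0.0225 = 15.37, rounded up to 16. All ten Table 2 entries reproduce with the same formula.

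**2. The interval it implies.** Half-width = 1.96 × √(0.09/n).
- n = 16: 1.96 × 0.0750 = 0.147, giving 0.753 to 1.047.
- n = 20: 1.96 × 0.0671 = 0.131, giving 0.769 to 1.031.

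Under a true 90%, the upper limit passes 100% in about 75% of samples at either n.

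**3. Its actual coverage at P = 0.90.** List the counts k of acceptable outcomes whose interval k/n ± 1.96√(p̂(1−p̂)/n) contains 0.90, then add their binomial probabilities.
- n = 16, k = 11 to 15: 0.0137 + 0.0514 + 0.1423 + 0.2745 + 0.3294 = 0.811.
- n = 20, k = 14 to 19: 0.0089 + 0.0319 + 0.0898 + 0.1901 + 0.2852 + 0.2702 = 0.876.

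Most of the missing coverage comes from samples with no Grade 3 or higher outcome, where the interval shrinks to 100% to 100%: 0.90^16 = 18.5% and 0.90^20 = 12.2%.

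**4. Scatter of the estimate.** The probability that p̂ lies within 0.15 of 0.90 at n = 16 (k = 12 to 16) is 0.0514 + 0.1423 + 0.2745 + 0.3294 + 0.1853 = 0.983. At n = 20 it is 98.9%. At n = 16 it falls to 92.1% if the true proportion is 0.85 and 89.0% if it is 0.80.

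**5. Valid intervals at P = 0.90.** Results are averaged over the binomial distribution.

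| n | Interval | Coverage | Mean half-width | Mean lower arm |
|---|---|---|---|---|
| 16 | Wilson | 93.2% | 0.147 | 0.224 |
| 16 | Clopper-Pearson | 98.3% | 0.164 | 0.245 |
| 20 | Wilson | 95.7% | 0.132 | 0.196 |
| 20 | Clopper-Pearson | 98.9% | 0.146 | 0.211 |

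**6. The most likely result at n = 20 (18/20).**
- Plan's formula: 0.900 ± 0.131, or 76.9% to 103.1%.
- Wilson: centre (0.90 + 3.8416/40)/(1 + 3.8416/20) = 0.9960/1.1921 = 0.836; half-width 1.96 × √(0.0045 + 0.0024)/1.1921 = 0.137. This gives 69.9% to 97.2%.
- Clopper-Pearson: the 2.5% point of Beta(18, 3) and the 97.5% point of Beta(19, 2), giving 68.3% to 98.8%.

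The plan's lower limit is above 70%; both valid lower limits are below it. The pattern is the same for 14/16: lower limits of 71.3% (plan's formula), 64.0% (Wilson) and 61.7% (exact).

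**7. Table 2 read as intervals.** Coverage is 36.9% at p = 0.95, N = 9 (zero width in 0.95^9 = 63% of samples), 81.1% at p = 0.90, N = 16, and 85.2% at p = 0.85, N = 22. The seven columns with p of 0.80 or below give about 92% to 95%. Read instead as the chance of an estimate within 15 points, the first three columns give 92.9%, 98.3% and 96.3%.

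**The case against.** The strongest defence is that the formula is a planning device, which section 7 presents only as a first indication before it moves to power curves and to 20 participants. Nothing in the documents says that the result will be reported as p̂ ± 1.96 SE. The criterion in section 5.1 uses the observed proportion and no confidence limit. On the target that the formula addresses, 16 participants do better than 95% at the assumed 90%.

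Much of this stands, and it rules out several stronger readings that a reader might infer:
- That 16 participants fail to deliver ±15%. At a true 90% they deliver it with 98.3% probability.
- That 20 is too few for the stated precision. At 20, Wilson and exact intervals both keep at least 95% coverage with a mean half-width below 0.15. Nor is a larger N the direct cure: coverage of the symmetric interval is 94.7% at n = 29 and 80.9% at n = 30.
- That Table 2 is miscalculated or that columns must go. Every entry reproduces.
- That the study's tolerability decision would change. As written, it does not depend on an interval.

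Two things survive. The plan draws an explicit 95% conclusion from this interval and offers no other, so a reader has nothing else to apply. And a mean half-width below 0.15 averages two unequal arms: at n = 20 the exact arms average 21.1 points below and 8.1 above. Only the lower one bears on 70%.

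**Conclusion.** The point holds as a fault in the interval and in the conclusion drawn from it. It does not extend to the formula's arithmetic or to the choice of 20. At P = 0.90 the nominal 95% is about 81% at n = 16 and 88% at n = 20. The stated ±15 points understates the uncertainty below the estimate, which averages about 20 points (Wilson) to 21 points (exact) at n = 20. A margin of ±15% also cannot by itself establish that results fall in the acceptable category.

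The coverage figures are values at a true 90%, the plan's own assumption, and they move with the true proportion: at n = 16, 92% at 0.85 and 56% at 0.95. The comparison with 70% assumes that someone will set a two-sided 95% interval beside the section 5.1 limit, which is natural but not prescribed. The grade-spacing rationale for e is unsound whichever interval is used.

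**What to change.** Keep 20 participants and change section 7 as follows:

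1. State that the primary proportion will be reported with a two-sided 95% Wilson or Clopper-Pearson interval, and name which one.
2. Replace the sentence claiming 95% confidence at 16 with the asymmetric precision expected at 20, for example that 18/20 acceptable gives 68% to 99% (exact).
3. Remove the grade-spacing justification for e. If a margin is kept, justify it by the precision wanted for the proportion.
4. Footnote Table 2 as a normal-approximation planning guide that is unreliable as an interval at p of 0.85 or above. The columns can stay.

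The cost is wording only, with no change to design, enrolment or data collection. The downside is that the stated precision becomes less favourable on the lower side, about 20 to 21 points instead of 15, and the plan will show openly that 18/20 does not exclude 70% with a valid 95% interval.
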